3.5 Definitions for the Purpose of this Study

Enrolled

For the purpose of collecting data and samples and reporting AEs, a subject will be considered enrolled beginning from the time the informed consent form is signed until the subject is considered “screen failure”, “discontinued”, or “completed”.

Randomized

Subjects are considered randomized when they meet all of the following criteria:

- Confirmation that the inclusion and exclusion criteria are met
- Consent is given and signed by the subject for the study
- Randomization number is assigned

Screen Failures

Subjects are considered screen failures when they meet 1 of the following criteria after signing consent:

- Screening tests reveal that the subject is ineligible
- Subject withdraws consent before being randomized

Discontinued

Subjects are considered discontinued when they meet 1 or more of the following criteria:

- Subject withdraws consent after being randomized (see Section 4.5)
- Subject is withdrawn after enrollment by investigator (see Section 4.7) including lost to follow-up

Completed

Subjects are considered completed when they are followed through Study Day 28 and complete the final study follow-up visit (Study Day 28) or die prior to this study visit.

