6.2.3 Study Day 0: Baseline Evaluation

Baseline evaluation must be completed prior to the first dose of study medication.

6.2.3.1 Clinical Data on Day 0

- Assessment for presence of complications (see Section 7.3.2)
- Vital signs, including SaO₂ (see Section 7.3.3)
- Assessment for AEs occurring after consent and prior to administration of study drug
- Severity of illness score (Sequential Organ Failure Assessment (SOFA) score or if < 24 months of age use Tal bronchiolitis score)

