8.2.2 Period of Assessment

All AEs that occur from the time the informed consent is signed through Day 28 will be documented, recorded, and reported. After the end of the protocol-defined AE reporting period, sites must report to the safety office serious, unexpected, clinically suspected adverse drug reactions if the study site staff becomes aware of the event on a passive basis.

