## Analysis Plan

### Subject Populations

Here we give the definitions for the populations that will be referred to for different analyses.

- Enrolled: all subjects that signed consent
- Intention to Treat (ITT) population: per protocol defined as all participants who are randomized and received at least 1 dose of the study drug, and for analysis the treatment group will be assigned as randomized.
- ITT age subgroups (only on specified analyses):
  - Adults  $\geq$  18 years
  - Children aged  $<18$  years
- ITT pediatric formulation subgroups (only on specified analyses; may be omitted depending on the number of subjects enrolled in each pediatric subgroup):
  - Children  $\geq$  13 years and  $<18$  years (children that take the adult tablet formulation)
  - Children aged  $<13$  years (as this is the age for pediatric formulation)
- ITT virology subgroups (only on specified analyses):
  - Influenza A or B
    - Influenza A
    - Influenza B
  - RSV
  - Human Metapneumovirus
  - Rhinovirus/Enterovirus
  - Adenovirus
  - Mycoplasma pneumoniae
  - Chlamydophila pneumoniae
  - Legionella pneumophila
  - Bordetella pertussis
  - Parainfluenza
  - Bocavirus
  - Coronavirus

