## Table and Figure presentation

Results in figures and tables will be presented

- all subjects (total)
- by randomized arm

Number in brackets [] represents corresponding table number

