## 8. Serious Adverse Events (ITT)

- Table: [14.3.2.1] Number (%) of subjects with an SAE by MedDRA System Organ Class (SOC) and Preferred Term (PT); number (%) of subjects with any SAE. In these tables, subjects with SAEs will be counted (e.g. counting a subject with multiple SAEs with the same PT only once for that PT).
- Table: [14.3.2.2] Number of SAEs by MedDRA System Organ Class (SOC) and Preferred Term (PT); number (%) of SAEs. In these tables, SAEs will be counted (e.g. counting multiple SAEs with the same PT within the same subject).

- List of SAEs: Randomized arm, days from randomization to first SAE experienced by a subject, subject ID, site, age, days from start of study drug to SAE, SAE (MedDRA SOC and PT, and verbatim description), severity grade, relatedness to study intervention, outcome (sort by randomized arm, subject ID, MedDRA SOC and PT and, if a subject has multiple SAEs, days from randomization to SAE). This listing will include any SAE that occur after day 28 and are reported.
- Listing of SAE after enrollment (informed consent) and not included in the ITT

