## 9. Adverse Events (ITT)

- Table: [14.3.1.1] Number (%) of subjects with an AE by MedDRA System Organ Class (SOC) and Preferred Term (PT) and severity grade; number (%) of subjects with any AE. In this table, subjects with AEs will be counted (e.g. counting a subject with multiple AEs with the same PT only once for that PT).
- Table: [14.3.1.2] Number of AEs by MedDRA System Organ Class (SOC) and Preferred Term (PT) and severity grade; number (%) of AEs. In this table, AEs will be counted (e.g. counting multiple AEs with the same PT within the same subject).
- List of AEs: Randomized arm, days from randomization to first AE experienced by a subject, subject ID, site, age, days from start of study drug to AE, AE (MedDRA SOC and PT, and verbatim description), severity grade, relatedness to study intervention, outcome (sort by randomized arm, subject ID, MedDRA SOC and PT and, if a subject has multiple AEs, days from randomization to AE). This listing will include any AE that occur after day 28 and are reported.
- Listing of AE after enrollment (informed consent) and not included in the ITT

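### The AE and SAE tables set no onset rule relative to first dose, so pre-dose events in later-dosed subjects count toward an arm and slightly dilute the safety comparison

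*SAP*

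**What the plan says.** **Collection.** Protocol 8.2.2 sets the AE window: "All AEs that occur from the time the informed consent is signed through Day 28 will be documented, recorded, and reported". Protocol 3.5 agrees; for AE reporting, "a subject will be considered enrolled beginning from the time the informed consent form is signed". The Day 0 baseline evaluation (Protocol 6.2.3.1) includes a dedicated item: "Assessment for AEs occurring after consent and prior to administration of study drug". Pre-dose events are therefore actively sought and will be in the database.

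**Tabulation.** SAP section 9 specifies "Number (%) of subjects with an AE by MedDRA System Organ Class (SOC) and Preferred Term (PT) and severity grade" (table 14.3.1.1) and a companion table of event counts (14.3.1.2). SAP section 8 specifies the same pair for SAEs (14.3.2.1 and 14.3.2.2). All four use the ITT population, defined in the SAP as "all participants who are randomized and received at least 1 dose of the study drug", with the addition that "for analysis the treatment group will be assigned as randomized". Results are shown in total and "by randomized arm".

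**What is absent.** Neither document defines a treatment-emergent event, and neither table section says from when events are counted. The AE and SAE listings do carry the number of days from start of study drug to each event. A further listing covers events after consent that fall outside the ITT.

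**The concern.** The third secondary objective is the safety and tolerability of NTZ, measured by cumulative incidence of AEs and SAEs. An event that starts before the first dose cannot have been caused by NTZ or by placebo. If the arm-wise tables include it, both arms gain the same background on average, and any true excess on NTZ looks proportionally smaller. In a safety comparison that is the unfavourable direction, since it makes a signal harder to see.

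The protocol suggests one route for such events. Baseline blood samples are taken before the first dose, but dosing need not wait for the results (6.2.3.2). A result beyond the renal or hepatic limits leads to stopping study drug (4.6), and a laboratory abnormality that requires an intervention, including stopping treatment, is reportable as an AE (8.2.1). A finding already present in a pre-dose sample could thus be tabulated under an arm, unless the site judges that it is not a worsening.

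**Working it through.** The documents give no AE or SAE rate, no pre-dose rate and no test for AEs, so there is no plan figure to reproduce. The check has two parts.

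**1. Can a pre-dose event reach the tables?**
- Collected? Yes, from consent (Protocol 8.2.2), with a specific pre-dose check (6.2.3.1).
- Subject in the population? Yes, if later given at least one dose (SAP, Subject Populations).
- Removed by an onset rule? No such rule appears in SAP sections 8 or 9.
- Diverted to the separate listing? No. The ITT is defined as a set of participants, so the listing of events outside the ITT covers undosed subjects and not early events in dosed ones.

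**2. How much would this matter?** (illustration; all rates are assumed)

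Inputs:
- Follow-up after dosing: 28 days = 672 h.
- Pre-dose period: 24 h. Protocol 6.2.1 allows no longer than 24 h to first dose but does not say from when; it also allows 12 h for screening. 12 h and 36 h are used as a range.
- True 28-day risks after dosing: 10% on placebo and 20% on NTZ, a ratio of 2.0 and a difference of 10 points.
- Constant hazard, with the same pre-dose share q in both arms.

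The 24 h period is 24/(24 + 672) = 3.4% of the total window.

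Pre-dose share: q = 1 − (1 − p)^(1/28), where p is the 28-day risk.
- p = 10%: q = 1 − 0.90^(1/28) = 0.0038, about 0.4%.
- p = 20%: q = 1 − 0.80^(1/28) = 0.0079, about 0.8%.

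The 10% figure is the natural one, because nobody has yet received the drug; 20% is an upper variant. Out of 145 per arm (290 randomised 1:1), these are about 0.5 and 1.2 subjects.

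Tabulated risk in an arm = q + (1 − q) × true risk.

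| q | NTZ | Placebo | Difference | Ratio |
|---|---|---|---|---|
| 0 | 20.0% | 10.0% | 10.0 points | 2.00 |
| 0.38% | 20.3% | 10.3% | 9.96 points | 1.96 |
| 0.79% | 20.6% | 10.7% | 9.92 points | 1.93 |

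Range for the window, scaling the exponent to (hours/24)/28: 12 h at p = 10% gives q = 0.19% and ratio 1.98; 36 h at p = 20% gives q = 1.19% and ratio 1.89.

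**Where it could be larger.** Take a single term with true risks of 5% and 15% (ratio 3.0). Under the constant hazard, q = 1 − 0.95^(1/28) = 0.18% and the ratio is 2.93. If events clustered before dosing so that q were 1%, the ratio would be 0.1585/0.0595 = 2.66; at 2% it would be 0.167/0.069 = 2.42. For a common outcome, such as any AE at 30% against 45% (ratio 1.50), q = 1% gives 1.48 and q = 2% gives 1.47.

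**The case against.** The case for leaving the tables alone has real substance.

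- **The SAP is silent on the start of counting.** A reader might infer that it prescribes counting from consent. It does not; that is what a literal programming of the tables would produce. This stands as a limit on the wording. It does not remove the point, because a programmer has no instruction to exclude pre-dose events.
- **The listing of events outside the ITT might already hold them.** The phrase could be stretched to mean events kept out of the ITT tables. Since the ITT is a set of participants, this reading is strained.
- **The protocol limits what is reportable.** Under 8.2.1, worsening upper respiratory symptoms need not be reported, gastrointestinal symptoms count only if new from baseline or worse, and laboratory abnormalities count mainly when they need an intervention. This stands, and it lowers the likely pre-dose count.
- **The pre-dose period is short.** Protocol 3.4 has treatment begin immediately after randomisation, and the 24 h limit is a maximum. This also stands.
- **The AE tables are descriptive.** Counts and percentages are planned, with no ratio or test, and on the difference scale the shift is under 0.1 point in the 24 h illustration. The listings show timing and relatedness for each event. All true, but the summary tables are what most readers will use for the safety comparison.

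**Conclusion.** The point holds as a small, correctable weakness. As written, the arm-wise AE and SAE tables do not exclude events that began before the first dose in subjects who were later dosed. Apart from chance imbalance, these events are equal between randomised, blinded arms. They cannot create a false signal on average; they can only dilute a true one. In the illustration a ratio of 2.0 appears as about 1.93 to 1.96. This rests on an assumed 24 h window, a constant hazard and assumed risks of 10% and 20%. Clustering before dosing, or a rare term, would make it larger, but the documents give no rate for either.

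Two stronger readings are tempting and are not supported. The first is that dilution is substantial because the hours before dosing are the most unstable of the admission. The documents give no event rate for that period, and exclusion 13 permits up to 60 h in hospital before enrolment, so Day 0 need not be the first day of admission. The second is that analysis as randomised materially biases safety through wrong kits. Kits are numbered, blinded and assigned in sequence (Protocol 5.1), and no misallocation rate is given. One such subject among 145 would be 0.7% of an arm. Treatment received is therefore a secondary point only.

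**What to change.** Amend SAP sections 8 and 9 before unblinding:

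1. Define a treatment-emergent AE or SAE as one with onset, or worsening in grade, at or after the first dose. Base tables 14.3.1.1, 14.3.1.2, 14.3.2.1 and 14.3.2.2 on it.
2. List pre-dose events in ITT subjects separately, by arm, using the days-from-start-of-study-drug field already in the listings.
3. State a rule for the day of first dose, because a field in whole days cannot by itself separate events before and after dosing on that day. One option is to treat an event as pre-dose if it was recorded at the Day 0 pre-dose check or has an onset time before the dose, and otherwise as post-dose. Date laboratory events by sample collection and not by when the result was reported.
4. As a secondary point, state that if any kit was misallocated, the safety tables will be presented by treatment actually received.

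The cost is SAP wording and a filter in the table programs. The plan already provides for the pre-dose check and the timing field, so no new assessment is needed, and efficacy analyses are unaffected.

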## 10. Laboratory Values (ITT and ITT age subgroups)

The following should be performed for the protocol specified collection days of 0, 3, 7, and 28. Figure and table that includes the min, 25%tile, 50%tile, 75%tile, max, change from baseline and % change from baseline at each day for each of the following lab values.

- CBC with differential white cell count (to include neutrophil, lymphocyte, and eosinophil percentages), hemoglobin, hematocrit, and platelets [14.3.5.1.x]
- Blood chemistries (creatinine, ALT/GPT, AST/GOT, total bilirubin, LDH, CRP) [14.3.5.2.x]

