8.2 Investigator Assessment of Adverse Events

8.2.1 Determination of Adverse Event

All worsening symptoms should be evaluated as potential adverse events:

- If a diagnosis is clinically evident (or subsequently determined), the diagnosis, rather than the individual signs and symptoms or lab abnormalities, will be recorded as the AE.
- Gastrointestinal tract SARI symptoms such as nausea, vomiting, or diarrhea, can be either related to SARI or the study drug. For this reason, if these gastrointestinal symptoms are new from baseline or worsen, they should be graded per the DAIDS toxicity table, and if they are new or represent a worsening grade then they should be reported as adverse events.
- Upper respiratory tract SARI symptoms (such as cough, sore throat, fatigue, headache, myalgia, rhinorrhea) can worsen due to the underlying disease. As these are unlikely to be related to the study drug, these do not need to be reported as Adverse Events.
- Any other new symptoms should be recorded as AEs.
- Symptoms present at baseline that resolve should have an end date (unless likely flu related). If they recur, the recurrence should be reported as an adverse event. Intermittent symptoms (such as cough, headache, rhinorrhea) would not be AEs if likely influenza related.

All worsening laboratory values should be evaluated as potential adverse events:

- If an abnormal laboratory finding is captured as a component of a diagnosis AE term that has already been recorded as a pre-study condition, the individual abnormal laboratory finding is **NOT** recorded as a separate AE.
- A laboratory abnormality should be reported as an AE only **if** it requires an intervention. Interventions include, but are not limited to, discontinuation of treatment, dose reduction/delay, additional assessments (including additional lab assessments), or concomitant treatment.
- In addition, any medically important laboratory abnormality may be reported as an AE at the discretion of the investigator who considers the test result clinically significant. This could include a laboratory result for which there is no intervention but the abnormal value is of clinical concern or suggests disease or organ toxicity. Grading should be based on the toxicity table where applicable.

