### Secondary Objectives:

1. Evaluate the clinical efficacy of NTZ + SOC vs. PCB + SOC with regards to:
  - Percent hospitalized at Study Day 3, 7, 14 and 28
  - Death by Study Day 28
  - Duration of clinical symptoms (defined in Section 7.3.1.2)
  - Duration of fever
  - Use of supplemental oxygen (or increase greater than baseline oxygen requirement)
  - Admission to ICU
  - Intubation/mechanical ventilation
  - Proportion of subjects who develop complications including pneumonia, respiratory failure requiring mechanical ventilation, acute respiratory distress syndrome (ARDS), sepsis, or bronchiolitis.
  - Time to resumption of normal activity
  - Antibiotic/antiviral use during hospitalization
  - Systemic corticosteroid use during hospitalization
  - Re-hospitalization within 28 days
2. Evaluate the virologic efficacy of NTZ + SOC vs. PCB + SOC with regards to:
  - Percent cessation of viral shedding at Study Day 3

3. Evaluate the safety and tolerability of NTZ assessed by:
  - Cumulative incidence and severity of adverse events (AEs)
  - Cumulative incidence of serious AEs (SAEs)
  - Cumulative incidence of laboratory abnormalities on Study Days 3, 7 and 28

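### The SAP plans no count of subjects with laboratory abnormalities, although their cumulative incidence is a stated safety objective

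*SAP*

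**What the plan says.** The safety objectives in Protocol 2.2 and in the SAP include, in the same words, "Cumulative incidence of laboratory abnormalities on Study Days 3, 7 and 28".

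SAP section 10 is the only section that analyses laboratory values. Its scope is "The following should be performed for the protocol specified collection days of 0, 3, 7, and 28", and its content for each analyte is a "Figure and table that includes the min, 25%tile, 50%tile, 75%tile, max, change from baseline and % change from baseline at each day". It defines no abnormality and names no grade or threshold. It plans no shift table and no count of subjects.

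SAP section 9 does count subjects: "Number (%) of subjects with an AE by MedDRA System Organ Class (SOC) and Preferred Term (PT) and severity grade". What enters that table is set by Protocol 8.2.1. It says "A laboratory abnormality should be reported as an AE only" if an intervention is required, and it explains that "Interventions include, but are not limited to, discontinuation of treatment, dose reduction/delay, additional assessments (including additional lab assessments), or concomitant treatment". There is a second route: "any medically important laboratory abnormality may be reported as an AE at the discretion of the investigator". On severity it says "Grading should be based on the toxicity table where applicable".

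Protocol 4.6 lists laboratory results that lead to stopping study medication. They concern estimated creatinine clearance, total bilirubin and AST/ALT. No haematology limit is listed. Protocol 5.2 sets a 5-day course.

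**The concern.** An incidence is a number of subjects over a denominator. The section 10 summaries describe the distribution of a measurement at a visit, and no incidence can be recovered from them. If the plan is followed exactly, one of the three stated safety objectives has no estimate in either arm.

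This matters because laboratory harm usually shows in the tail: a few more subjects with clearly abnormal values, not a shift of the whole distribution. The number of such subjects per arm is the figure a safety reader needs.

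Baseline matters too. Renal and liver disease are excluded by self-report (Protocol 4.4), and baseline results need not be available before dosing starts (Protocol 6.2.3.2). Some subjects may therefore enter with abnormal values. The maximum at a follow-up visit does not separate those from abnormalities that arose on study.

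**Working it through.** The plan states no figure for laboratory abnormalities, so there is none to reproduce. The check sets the objective beside each planned output and then adds a small illustration.

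**Step 1: what each output supplies.**

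- *SAP 10, quartiles per visit:* the centre and spread of the values. No count.
- *SAP 10, minimum and maximum per visit:* the most extreme value in the arm at that visit. One subject or many could lie behind it, and the same subject could recur across visits.
- *SAP 10, change and percent change from baseline:* the statistic is not named. No threshold is applied, so no count results.
- *SAP 9, adverse event tables:* subjects are counted by preferred term and grade, but only for abnormalities reported as adverse events. Protocol 8.2.1 also has a diagnosis recorded in place of the laboratory finding where one is evident, and does not separately record a finding that belongs to a recorded pre-study condition.
- *SAP 5, listing of incomplete treatment:* shows subjects who stopped early, with the reason. It is a listing, and it covers only the dosing period.

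None of these is an incidence of laboratory abnormalities.

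**Step 2: which abnormalities have an assured route into a count.** Crossing a Protocol 4.6 limit during dosing stops study drug. Protocol 8.2.1 names discontinuation of treatment as an intervention, so a new or worsened value of this kind is reportable. Dosing lasts 5 days. Of the three scheduled follow-up draws (Days 3, 7 and 28), only Day 3 falls within the course. Three groups have no assured route:

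- haematology values
- values first abnormal at Day 7 or Day 28
- abnormalities that need no action and that the investigator does not report

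The second and third of these can include renal and liver values.

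**Step 3: illustration.** Input from the documents: 290 subjects randomized 1:1, so 290 / 2 = 145 per arm. The documents give no rate of severe values, so the rates p below are assumptions. The expected count is 145 × p, and the chance of at least one is 1 − (1 − p)^145.

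| Assumed rate p | Expected subjects | Chance of at least one |
|---|---|---|
| 1% | 1.45 | 77% |
| 2% | 2.9 | 95% |
| 5% | 7.25 | 99.9% |
| 10% | 14.5 | over 99.9% |

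Take 1% in one arm and 5% in the other. Both arms contain at least one severe value with probability 0.767 × 0.9994 = 0.767. The expected counts differ fivefold (1.45 against 7.25), yet in about 77% of trials both arms would show a severe maximum.

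**Step 4: reaction of the planned statistics.** In a simulated set of 145 positive values, the minimum, quartiles and maximum were 8.3, 18.9, 24.5, 30.4 and 68.0. The top 1, 4 or 10 values were then replaced with 400. In all three cases the first four figures did not change and the maximum became 400. The summary is therefore identical for 1, 4 and 10 affected subjects.

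The quartiles stay exactly fixed only because the affected subjects were already above the 75th percentile. About 145 / 4 ≈ 36 values lie above it. If 7 subjects moved from below it to far above it, 36 − 7 = 29 of the former upper values would remain above the new quartile. Since 29 / 145 = 20%, the new 75th percentile would sit near the former 80th. That is a small shift, and it still gives no count.

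**The case against.** The strongest case on the other side has four parts.

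- *Section 10 is not blind to extremes.* It lists the minimum and maximum by arm and visit, and a figure of unspecified type that might show individual values. This stands. A reader might infer that rare severe abnormalities would be invisible, or that the plan offers only quartiles and means. The documents do not support that: the extremes are listed, and no mean is named.
- *The adverse event rule is broad.* An extra laboratory test counts as an intervention, and there is a discretionary route for medically important values. Severe abnormalities are the most likely to qualify. This also stands. A reader might infer that the adverse event tables leave out most abnormalities, but no figure in the documents says what share is left out.
- *Severe renal and liver values during dosing are largely caught.* They stop study drug, can be reported and counted as adverse events, and appear with a reason in the SAP section 5 listing. This stands for the dosing period and those analytes only.
- *The listed safety endpoint is the chemistry and haematology assessments themselves, which section 10 does summarize.* True, but the objective that this endpoint serves asks for an incidence.

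What survives is the mismatch itself. No planned output counts subjects with laboratory abnormalities independently of the adverse event reporting decision.

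**Conclusion.** The concern holds in this form: the protocol and SAP state an incidence objective for laboratory abnormalities, and the SAP plans no analysis that estimates it. The section 10 summaries show that an extreme value occurred, not how many subjects had one or whether it was new. The adverse event tables hold a subset that depends on intervention or on investigator judgment.

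The mismatch follows from the text alone and rests on no assumption. Its practical size does rest on assumptions, because the documents give no abnormality rates. The 1% to 10% rates and the simulated values are illustrations. They show how the planned statistics behave and do not predict harm from nitazoxanide.

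The point concerns the completeness of the safety analysis. It does not affect the primary efficacy inference. It should be corrected before unblinding, since the choice of thresholds and grades should not be open once results by arm are known.

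**What to change.** Keep the section 10 summaries and add one table by arm, with these specifications:

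- Number and percentage of subjects with a new abnormality, or one that worsened from baseline, by grade on the DAIDS scale that Protocol 8.2.3.1 already adopts, where that scale covers the analyte.
- Columns for Days 3, 7 and 28, and cumulatively to Day 28 with each subject counted once at the worst grade.
- A stated denominator (for example, subjects with a baseline value and at least one later value), and a statement of whether unscheduled results count towards the cumulative column.
- Descriptive rows counting subjects past the laboratory limits already written in Protocol 4.6. These rows only count. They imply nothing about treatment, in particular after dosing has ended.

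The cost is modest but is more than one simple table. Several analytes, visits and grades must be programmed. Testing is done in local laboratories (Protocol 7.1.1), so upper limits of normal are needed for each site. A formula for estimated creatinine clearance must be stated, because the documents give none. The laboratory results themselves are already collected, and no study procedure changes.
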